3 STUDY METHODOLOGY

3.1 Study Design

This is a prospective, single-center study to evaluate the everlinQ System when used to create an endoAVF in hemodialysis patients. A total of up to 50 subjects will be enrolled and will undergo an endoAVF creation procedure using the everlinQ System. All subjects will be followed for up to 12 months post index procedure based on Investigator's discretion.

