3.3 Study Endpoints

Study endpoints will be summarized using descriptive statistics. There are no formal hypothesis tests associated with these endpoints.

- **Technical success:** Verification that an endoAVF has been created and remains patent 1-7 Days after the index procedure. Patency will be determined by experienced examiner as the presence of a bruit that is detected with stethoscope, or presence of thrill, or via Duplex Ultrasound, or via angiogram.
- **Fistula Maturation:** defined as endoAVF that is free of stenosis or thrombosis, with brachial artery flow of at least 500 ml/min and at least 4 mm vein diameter (as measured by duplex ultrasound) OR patient was dialyzed using 2 needles.
- **The Time to Fistula Maturation:** the number of days between the date of AVF creation and the date of endoAVF maturation (based on primary efficacy endpoint definition of maturation).
- **Duration of Central Venous Catheter Exposure:** The rate of CVC use per enrolled subjects at 30-45 Days and other follow-up visits. The analysis will be performed for pre-dialysis and on dialysis patients, as applicable.
- **EndoAVF-related Re-intervention Rate:** The re-intervention rate for endoAVF (defined as any intervention required to maintain or re-establish patency) will be calculated at each available follow-up visit post index procedure.
- **Primary Patency:** The primary patency rate will be determined via Kaplan-Meier methods and based on the time of endoAVF creation until any intervention designed to maintain or reestablish patency or endoAVF abandonment.
- **Secondary Patency:** The secondary patency rate will be determined via Kaplan-Meier methods and based on the time of endoAVF creation until access abandonment. Abandonment due to renal transplant receipt will not be included in this endpoint assessment.
- **Safety:** The safety endpoint is the percentage of patients who experience one or more serious device -related adverse events during the first 3 months following AVF creation.

Additional exploratory analysis:

- Rate of serious procedure-related events will be reported at 3 months.
- Rate of serious device-related event rate will be reported at 3 months.
- Rate of device and/or procedure-related infections at 3 months.
- Arterial and arterialized vein flow rates and diameters will be measured via DUS at 30-45 Days and at each available follow-up visit post index procedure.

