4 STUDY SCREENING AND FOLLOW-UP PROCEDURES

Patients are required to undergo a thorough screening evaluation prior to the index procedure and return for evaluations according to the study follow-up schedule indicated in Table 1. Study data will be collected on case report forms (CRFs) provided by the Sponsor. Any site's standard of care tests may be done outside of the study (e.g., prior to study participation).

Table 1: Schedule of Study Procedures

Assessment	Screening	Index Procedure	Post Index Procedure				
			1-7 Days	30-45 Days	3 Months	6 Months (Optional) ¹	12 Month (Optional) ¹
Compliance window	-30 days	Day 0	1-7 days	30-45 days	Anniversary date + 14 / -7 days	Anniversary date + 45 / -15 days	Anniversary date + 60 / -30 days
Informed Consent	X						
History, Physical Exam, Laboratory Evaluation	X						
Ultrasound Evaluation	X	X ¹	X	X	X	X ¹	X ¹
Angiography/Venography	X ¹	X	X ¹	X ¹	X	X ¹	X ¹
Adverse Events		X	X	X	X	X	X
Dialysis Access Data				X ²	X ²	X ²	X ²

¹ Optional visit at the discretion of the Primary Investigator
² Will be obtained after dialysis is initiated using endoAVF created by the everlinQ System.

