4.4.2 Patient Disposition

The Patient Disposition Case Report Form should be completed whenever a patient exits the study. This includes patients enrolled in the study who:

- complete the study protocol,
- withdraw from the study,
- are lost to follow-up,
- are deceased,
- have other reason(s) for exiting the study.

4.5

Adverse Events

For the purpose of this protocol, an AE will be defined as any adverse medical change (i.e., *de novo* or increased severity in a preexisting condition) from the subject's baseline condition that occurs during the course of the clinical study, after starting treatment, whether considered treatment-related or not. "Treatment" includes all investigative or commercially-approved products administered according to the Study Protocol.

Any pre-planned procedures, interventions, etc. or expected progression of pre-existing conditions (e.g., cancer progression) will not be considered AEs for this study. In addition, normally expected symptoms caused by the treatment are not considered an AE for this study. These may include but are not limited to:

- Transient arterial spasm resolving spontaneously OR with medication only.
- Minor discomfort or bruise at the arterial access place.
- Small amount of bleeding at point of arterial access.
- Transient numbness, tingling or coolness that resolved within 4 weeks post index procedure.
- Bruising at the AVF creation site.
- Side effects of standard-of-care medications.
- Hematoma at the arterial and/or venous access site(s) managed prior to patient discharge and did not adversely affect patient discharge.

Only AEs that are relevant to index procedure, study device, access site or AVF will be collected in the study. For example, if the patient has knee replacement or undergo hysterectomy, these events will be considered as non-study related and will not be required to be recorded via Adverse Event form.

AE Type	Definition

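### Catheter use is expressed per enrolled subject at every visit, so incomplete follow-up can lower the reported rate but never raise it, mainly at the optional 6- and 12-month visits

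*Combined protocol and SAP*

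**What the plan says.** Section 3.3 heads the endpoint as a duration of catheter exposure but defines it as a rate at visits: "The rate of CVC use per enrolled subjects at 30-45 Days and other follow-up visits". It adds: "The analysis will be performed for pre-dialysis and on dialysis patients, as applicable". It does not say whether dialysis status is taken at enrollment or at each visit.

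Section 3.1 sets the maximum size: "A total of up to 50 subjects will be enrolled and will undergo an endoAVF creation procedure using the everlinQ System". On follow-up it says: "All subjects will be followed for up to 12 months post index procedure based on Investigator's discretion". In Table 1 (Section 4) the 6- and 12-month visits carry the footnote "Optional visit at the discretion of the Primary Investigator"; the 30-45 day and 3-month visits do not. A second footnote governs dialysis access data: "Will be obtained after dialysis is initiated using endoAVF created by the everlinQ System".

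Section 4.4.2 captures exits: "The Patient Disposition Case Report Form should be completed whenever a patient exits the study". Nothing links that form to the denominator of any endpoint. A transplant rule exists for secondary patency only: "Abandonment due to renal transplant receipt will not be included in this endpoint assessment". Section 5 provides descriptive summaries and no rule for missing data.

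**The concern.** Only a subject whose catheter status is ascertained can be counted as a CVC user, yet the denominator is everyone enrolled. Where follow-up is incomplete and nothing is imputed, each subject without an assessment has the same arithmetical effect as a subject without a catheter. Because the last two visits are optional, unequal attendance is part of the design.

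The error runs in one direction and favors the device. The study has no hypothesis tests, so no error rate or power is affected. For the same reason the descriptive rate is the whole result for this endpoint, and a reader comparing visits could take falling attendance for falling catheter use.

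Two related gaps affect the remedy. If CVC status is taken from the dialysis access data, subjects still relying on a catheter may have no record even when they attend. And the pre-dialysis and on-dialysis groups have no stated reference time.

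**Working it through.** The plan gives no expected CVC rate or attendance, so there is no figure of its own to reproduce.

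**Inputs.** N = 50 enrolled (Section 3.1, maximum). Assumptions: all 50 are on dialysis; CVC use p = 30% at every visit; attendance a is unrelated to CVC use; nobody has died, been transplanted or exited, so every unseen subject is simply of unknown status.

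**Formulas.** Seen n = aN. CVC users seen x = pn. Rate per enrolled = x/N = p × a. Rate among those seen = x/n. Bounds = x/N (all unseen catheter-free) to (x + N − n)/N (all unseen on a CVC).

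| Attendance | Seen | CVC users seen | Per enrolled | Among seen | Bounds |
|---|---|---|---|---|---|
| 100% | 50 | 15 | 15/50 = 30% | 30% | 30% to 30% |
| 80% | 40 | 12 | 12/50 = 24% | 30% | 24% to (12+10)/50 = 44% |
| 60% | 30 | 9 | 9/50 = 18% | 30% | 18% to (9+20)/50 = 58% |
| 40% | 20 | 6 | 6/50 = 12% | 30% | 12% to (6+30)/50 = 72% |

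The per-enrolled rate is always the lower bound.

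**Other prevalences.** At 50% attendance, true rates of 20%, 40% and 60% are reported as 5/50 = 10%, 10/50 = 20% and 15/50 = 30%.

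**If attendance depends on CVC use.** Take 15 users among 50 and 10 subjects unseen.
- All 10 are catheter-free: per enrolled 15/50 = 30%, unchanged; among seen 15/40 = 37.5%.
- All 10 are CVC users: per enrolled 5/50 = 10%; among seen 5/40 = 12.5%.

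The per-enrolled rate thus lies between 10% and 30% and never exceeds the true 30%. The rate among those seen can err either way, so replacing the denominator is not enough without bounds.

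**Effect of the Table 1 footnote.** Suppose all 50 attend, CVC status comes only from dialysis access data, and the 35 catheter-free subjects all have a record. If none of the 15 users has begun dialysis through the endoAVF, a denominator of subjects with recorded access gives 0/35 = 0%; if all 15 have begun, it gives 15/50 = 30%. The new denominator is safe only if catheter status is recorded independently of endoAVF use.

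**The case against.** The strongest reply is that the phrase about enrolled subjects names a population and does not fix N at each visit. Section 4.2 separates consented from enrolled subjects, and Section 5 describes discrete variables by percentages of responses, which suggests subjects with data. This reading is possible but not decisive. In the same Section 3.3, re-intervention and the ultrasound measurements are tied to whichever follow-up visits are available, and patency uses Kaplan-Meier; the CVC endpoint has neither device. If the milder reading is intended, the plan should say so before results are seen.

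Four stronger readings are tempting, and the documents do not support them.
- A reader might infer that the plan instructs unseen subjects to be scored catheter-free. No such rule is written; it is the consequence of a fixed denominator without imputation.
- A reader might infer that the rate must fall whenever attendance falls. It does not if those missing have no catheter.
- A reader might infer that catheter avoidance is the reason for the trial. Section 1 presents catheters as a consequence of failed maturation; the stated aims are better maturation and patency and a less invasive procedure.
- A reader might infer that the pre-dialysis rate is near zero by construction. That holds only if status is taken at the visit. Inclusion criterion 3 uses the term for status at entry, so the enrollment reading is at least as natural.

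It also stands that the 30-45 day and 3-month visits are required, so the problem is smaller there.

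**Conclusion.** The point holds. Followed as written, the endpoint can understate catheter use through incomplete follow-up and cannot overstate it that way. The exposure is mainly at the optional 6- and 12-month visits. Splitting by dialysis status does not cure it, since the same problem recurs within each group.

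The size cannot be taken from the documents. A constant 30% reported as 12% at 40% attendance rests on all 50 subjects being on dialysis and on attendance being unrelated to CVC use. Since pre-dialysis patients are eligible, the first assumption will probably not hold exactly. The direction of the error does not depend on either assumption. This should be corrected, but it concerns one of several descriptive endpoints and does not threaten the study as a whole.

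**What to change.** 1. In Section 3.3, define the denominator at each visit as subjects who are alive, not transplanted, still in the study, on hemodialysis and of known CVC status. Beside it, show how many enrolled subjects are excluded, by reason. Give bounds that count those of unknown status first as all catheter-free, then as all on a CVC.
2. Record CVC in place and in use (yes/no) for every subject at every attended visit, whether or not dialysis through the endoAVF has begun, and amend the Table 1 footnote to match. Without this step, the first change could drop the catheter-dependent subjects.
3. Define the pre-dialysis and on-dialysis groups by status at enrollment. For those pre-dialysis at enrollment, report the percentage of hemodialysis starters who started on a CVC.

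The cost is a short rewording, one extra CRF item and one extra table column, with no new visits. Late CVC rates will probably be less favorable and will be less precise: at 30% use, the standard error is √(0.30 × 0.70/20) = 10 percentage points with 20 subjects assessed, against √(0.30 × 0.70/50) = 6.5 with 50.

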An AVF is traditionally created during a surgical procedure under general anesthesia. A surgical incision is made in the forearm or upper arm, followed by identification of target arteries and veins for surgical connection. Frequently, prior to the procedure, the vessels are mapped using duplex ultrasound imaging, allowing for pre-operative vessel diameter measurement and vessel selection. Typically, the radial artery or brachial artery and the cephalic vein or basilic veins are selected. The target vessels are carefully dissected and mobilized, and the vein is transected. An arteriotomy is created, and an anastomosis is sewn between the vein and the artery. After completion, the flow is verified using palpation and ultrasound, and the incision is closed. Over the course of the following 1 - 3 months, the AVF gradually matures, that is, the vein dilates and accepts increased flow sufficient for hemodialysis.

Though there is widespread agreement that the AVF is the preferred method of vascular access, 28 – 60% of AVFs do not successfully mature and are rendered unusable for hemodialysis.^{10,12} This has unintended consequences for patients in immediate need of hemodialysis, since a tunneled dialysis catheter must often be placed. Catheters are associated with higher morbidity, mortality, and costs and are therefore considered a last resort.¹¹

To improve on these results, and decrease the invasiveness of the procedure, a new tool and method for creation of an AVF has been developed, called everlinQ system. The system uses two devices,

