3.5.1 Inclusion Criteria

1. Eligible for a native arteriovenous fistula.
2. Adult (age >18 years old).
3. Established, non-reversible kidney failure requiring hemodialysis (including pre-dialysis patients).
4. Target vein diameter(s) ≥ 2.0 mm or large enough to accommodate device diameter.
5. Target artery diameter ≥ 2.0 mm or large enough to accommodate device diameter.
6. Estimated life expectancy > 1 year.
7. Patient is free of clinically significant conditions or illness within 30 days prior to the AV fistula that may compromise the procedure

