4.2 Screening Evaluation

All patients considered for enrollment must undergo a thorough screening evaluation prior to the scheduled treatment with the everlinQ System. The screening evaluation includes:

- Collection of demographic data;
- A medical history and physical exam;

- A laboratory evaluation (i.e. blood tests); and
- A duplex ultrasound and optional angiography/venography assessment.

There will be a final assessment of the suitability of the patient's study eligibility due to vascular anatomy or other criteria made at the time of the index procedure and thus, there may be some consented subjects who are determined to be ineligible who will not be enrolled in the study.

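### The CVC endpoint is a rate at each visit that takes no account of catheter status at the index procedure and fixes no time for dialysis status, so the on-dialysis rate mixes catheters removed with catheters newly placed

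*Combined protocol and SAP*

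**What the plan says.** Section 3.3 titles the endpoint "Duration of Central Venous Catheter Exposure" but defines it as "The rate of CVC use per enrolled subjects at 30-45 Days and other follow-up visits". The next sentence gives the only subdivision: "The analysis will be performed for pre-dialysis and on dialysis patients, as applicable". No time is given at which a subject counts as pre-dialysis or on dialysis, and neither removal nor new placement of a catheter is mentioned.

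Both kinds of patient may enter. Item 3 of section 3.5.1 reads "Established, non-reversible kidney failure requiring hemodialysis (including pre-dialysis patients". The eligibility criteria neither exclude nor stratify by an existing dialysis catheter.

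On data capture, section 4.2 lists "A medical history and physical exam" at screening without naming catheter or dialysis status. Table 1 has no row for CVC status. Its dialysis access row starts at 30-45 days, with the footnote "Will be obtained after dialysis is initiated using endoAVF created by the everlinQ System". Section 5 adds no rule for this endpoint.

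**The concern.** The Introduction gives the need for a tunneled catheter as a main harm of a fistula that fails to mature. This endpoint is the one that should show whether the endoAVF spares patients that harm.

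A subject with a catheter at a visit may have had it at index and not yet lost it, or may have received it since because the fistula was not usable in time. These mean different things about the device, and a rate at the visit counts them alike. There is no control arm, so status at index is the natural reference, and the endpoint does not use it. Because the time of the dialysis split is left open, the same data can also yield different group rates.

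**Working it through.** The plan states no CVC rate, target or sample size calculation, so there is no figure to reproduce. The check is an accounting identity.

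**Inputs**
- Enrolment of up to 50 (section 3.1: "A total of up to 50 subjects will be enrolled and will undergo an endoAVF creation procedure using the everlinQ System").
- Pre-dialysis and on-dialysis subjects both eligible (section 3.5.1, item 3).
- Catheters at index, removals, new placements and group sizes: not in the documents. All such counts below are assumptions.

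**Identity.** In a group of n subjects, let B have a CVC at index. By the visit, R of those B are without one, and P of the other n − B have one. Then

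visit rate = (B − R + P) / n.

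One observed rate fixes only the difference P − R, for a given B.

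**Status fixed at index, pre-dialysis group.** If no pre-dialysis subject has a catheter at index (an assumption), then B = R = 0 and the rate is P/n. That is new placement and can be read as such.

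**Status fixed at index, on-dialysis group.** Take n = 30, B = 24 and an observed 18/30 = 60%.
- (24 − 6 + 0)/30 = 18/30: 6/24 = 25% removed, 0/6 = 0% new.
- (24 − 10 + 4)/30 = 18/30: 10/24 = 42% removed, 4/6 = 67% new.

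The range depends on B. With 18/30 held fixed, P = R − (B − 18), and P cannot exceed 30 − B:

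| B of 30 (assumed) | Possible R | Removed | Newly placed |
|---|---|---|---|
| 20 | 2 to 12 | 10% to 60% | 0/10 to 10/10 |
| 24 | 6 to 12 | 25% to 50% | 0/6 to 6/6 |
| 30 | 12 | 40% | none possible |

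The ambiguity grows with the number of on-dialysis subjects who have no catheter at index. It vanishes if all of them have one.

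**Status taken at the visit.** Suppose 20 subjects are pre-dialysis at index without a catheter, and 6 start dialysis on a CVC by the visit.
- By index status: 6/20 = 30%.
- By visit status: the 6 leave the group, so 0/(20 − 6) = 0/14 = 0%.

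A second set of assumed counts shows both groups moving. At index, 25 are pre-dialysis (no CVC) and 25 on dialysis (20 with a CVC). By the visit, 10 pre-dialysis subjects have started dialysis on a new CVC and 10 of the 20 index catheters are out.
- By index status: 10/25 = 40% and (20 − 10)/25 = 40%.
- By visit status: 0/15 = 0% and (10 + 10)/(25 + 10) = 20/35 = 57.1%.

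The total is 20/50 = 40% either way.

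**Data capture.** The endpoint needs CVC status for every enrolled subject at each visit. The only access row in Table 1 begins once dialysis through the endoAVF has started. A subject dialyzed only by catheter therefore has no scheduled access record under that row, although such a subject belongs in the numerator.

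**The case against.** The strongest reply is that the planned split already does much of the work. A reader might infer that the endpoint cannot separate removal from new placement at all, for example because a pooled 20/50 = 40% fits both 4/24 removed with 0/26 new and 14/24 removed with 10/26 new. The plan does not stop at the pooled rate. With 30 on dialysis (24 with a CVC) and 20 pre-dialysis, and all new placements among pre-dialysis subjects, the first case gives 20/30 = 67% and 0/20 = 0%. The second gives 10/30 = 33% and 10/20 = 50%. The split tells them apart. This stands, and it confines the mixing to the on-dialysis group when status is fixed at index and pre-dialysis subjects have no catheter then.

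Second, status at entry is arguably the ordinary reading, since section 3.5.1 uses the term pre-dialysis as an enrolment category. A reader might infer that the pre-dialysis rate is zero by construction. That follows only if status is taken at the visit, which the plan does not say. It does not exclude it either.

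Third, a reader might take "Over the course of the following 1 - 3 months, the AVF gradually matures" to show that most index catheters would still be in place at 30-45 days. That sentence describes the traditional surgical fistula. The plan gives no such course for the endoAVF, and section 2.1 suggests that its maturation may be better. The point does not rest on it.

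Fourth, the screening history, or case report forms that are not in the documents, may record a catheter at baseline. The documents therefore do not show that the information is absent, only that the protocol neither requires it nor uses it. The missing baseline entry in the dialysis access row is weak evidence by itself, because that row concerns dialysis through the study fistula.

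Finally, this is a single-center, single-arm, descriptive pilot with no decision rule on CVC use. That limits the weight of the point but does not remove it: a descriptive result is useful only if it can be interpreted.

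**Conclusion.** The point holds in limited form. The endpoint is a visit rate with no reference to catheter status at index and no fixed time for dialysis status. Under the more favorable reading, the pre-dialysis rate is interpretable and the on-dialysis rate is not: an assumed 18/30 fits removal anywhere from 25% to 50% when 24 of 30 have a catheter at index, and from 10% to 60% when 20 of 30 do. Under the other reading, the pre-dialysis rate falls toward zero as subjects who start on a catheter change group (30% against 0% on assumed counts).

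The counts are illustrations. The actual size depends on the case mix at index, which the documents do not give. No error rate, power or sample size is affected, only what can be concluded about catheter avoidance. This is a cheap improvement.

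**What to change.** In section 3.3, define the groups by dialysis status (pre-dialysis or on dialysis) and by CVC status (in place or not), both at the index procedure, and keep each subject in that group throughout. Name both items among the data recorded at screening or index. At each visit report:

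- (a) among subjects with a CVC at index, the percentage whose CVC has been removed;
- (b) among subjects without a CVC at index, the percentage with a CVC placed since index.

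Add CVC status to Table 1 at every follow-up visit for all subjects, whether or not the endoAVF is in use, because the dialysis access row does not provide it.

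With the assumed 30 on-dialysis subjects, the two cases that share 18/30 would then read 6/24 and 0/6 against 10/24 and 4/6. The cost is two baseline items, one CVC item per visit and reworded text, with no added visits or procedures. Denominators become smaller: in a group of 6, one subject moves the percentage by 1/6, about 17 points, so counts should be shown beside percentages.

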2.2 Risks

Many of the potential risks and complications associated with the everlinQ System and procedure are similar to the risks expected for CKD patients undergoing surgically created arteriovenous fistula (AVF) procedures. The potential risks related to the everlinQ System and procedure are similar to surgical AVF creation and may include but not limited to:

- Bruising
- Numbness, tingling and/or coolness in the fistula extremity
- Occlusion/stenosis (AVF clots)
- Thrombosis (AVF completely clotted and cannot be used)
- Failure to mature (AVF can never be used)
- Additional procedures (interventions)
- Venous hypertension (arm swelling)
- Aborted or longer procedure
- Swelling, irritation or pain
- Bleeding, hematoma (a solid swelling of clotted blood within the tissues) or hemorrhage (an escape of blood from a ruptured blood vessel)
- Wound problem
- Fever (pyrogenic reaction)
- Steal or ischemia (not enough blood flow to hand)
- Embolism (blood clot or device piece)
- Infection (local or in the blood (bacteremia))
- Increased risk of congestive heart failure (heart fails due to increased flow from AVF)
- Vessel, nerve or AVF damage or rupture
- Pseudoaneurysm (leaking hole in artery that forms blood clot on outside of it)
- Heart problems such as arrhythmias (abnormal beats) that can be caused due to high levels of potassium in the blood (mostly due to CKD and not the TVA device or procedure)
- Death (mostly due to CKD related complications not the TVA device or procedure)
- Burns
- Problem due to sedation or anesthesia
- Sepsis (systemic inflammatory reaction)
- Toxic or allergic reaction
- Electrocution

In addition, fistula infiltration injury due to needle cannulation of the fistula is also a known risk/event.

Most of these potential risks also exist for creation of standard (surgical) AVFs. There may also be other risks related to use of the everlinQ System and procedure that are not listed or that are not known at this time. This study will help characterize the adverse events associated with the everlinQ System.

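### The primary patency curve has no event for an occlusion found on examination, abandonment is undefined and undated, and the transplant exemption applies to secondary patency only

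*Combined protocol and SAP*

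**What the plan says.** All the relevant rules are in section 3.3 of the combined protocol and SAP.

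- **Primary patency** is a Kaplan-Meier estimate "based on the time of endoAVF creation until any intervention designed to maintain or reestablish patency or endoAVF abandonment". Those are its only two events.
- **Secondary patency** is a Kaplan-Meier estimate whose only event is abandonment of the access. It alone adds: "Abandonment due to renal transplant receipt will not be included in this endpoint assessment."
- **Technical success**, assessed at 1-7 days, treats patency as an examination finding: "Patency will be determined by experienced examiner as the presence of a bruit that is detected with stethoscope, or presence of thrill", with duplex ultrasound or angiogram as further alternatives.
- **Maturation**, in its ultrasound limb, is "defined as endoAVF that is free of stenosis or thrombosis".

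Abandonment appears only in the two patency definitions, with no definition, no rule on who declares it and no date. Section 5 (Data Analysis) adds no event, dating or censoring rule.

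Section 4 has patients "return for evaluations according to the study follow-up schedule indicated in Table 1". Table 1 requires ultrasound at 1-7 days, 30-45 days and 3 months; the 3-month window is "Anniversary date + 14 / -7 days". The 6- and 12-month columns carry the footnote "Optional visit at the discretion of the Primary Investigator". Section 3.1 sets enrolment at up to 50.

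**The concern.** The plan collects the finding that shows loss of patency but does not let it end patency. An access that is occluded on the 30-45 day ultrasound, and is neither treated nor formally given up, has no primary event. If someone acts on it later, the event falls on the later date. Both make primary patency read high.

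The transplant rule works the other way. A working access given up because the patient received a kidney is a primary failure on the literal text but is exempt from secondary patency. That makes primary patency read low for a reason unrelated to the device.

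The study is descriptive and has no hypothesis test, so no error rate or power is affected. At stake are the reported percentages and whether a second analyst could reproduce them. Section 2.1 expects patency to be set against historical data, which calls for a stable event definition.

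**Working it through.** The plan states no patency rate, event count or sample-size derivation, so there is no figure to reproduce. The check has two parts: what the text does with particular cases, and how much one case moves the estimate.

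**Cases under the literal text of section 3.3**

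| Case | Primary patency | Secondary patency |
|---|---|---|
| Occluded at 30-45 days, untreated, not declared abandoned | No event; stays patent | No event; stays patent |
| Occluded at 30-45 days, intervention after month 3 | Event after month 3; patent at month 3 | No event |
| Patent access given up because of transplant | Failure | Exempt; censored or dropped not stated |
| Access given up, no date recorded | Failure, date open | Failure, date open |

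Other data do not settle the dates. Under Table 1, dialysis access data start only once dialysis runs through the endoAVF, so they cannot date the loss of a fistula never used; pre-dialysis patients are eligible (section 3.5.1). The exit reasons in section 4.4.2 name neither transplant nor abandonment.

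**Size per subject.** With no censoring before time t, the Kaplan-Meier estimate is 1 - d/N, where d is the number of events by t. One reclassified subject moves it by 1/N: 1/50 = 2.0 points, 1/40 = 2.5, 1/30 = 3.3. Only the maximum of 50 comes from the documents.

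**Illustration: occlusion.** Assume N = 50, 10 listed events by day 90, and k accesses found occluded at day 40 with no treatment or declaration.

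- As written: 1 - 10/50 = 80.0% for every k.
- Occlusion counted at the examination: 1 - (10 + k)/50 = 78.0% (k = 1), 74.0% (k = 3), 70.0% (k = 5).
- Occluded accesses censored at the examination, a third possible choice: 79.7%, 79.2%, 78.5%.

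**Illustration: transplant.** Assume the same 10 events, t transplant-related abandonments at day 200, and full 12-month follow-up.

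- Counted as primary failures: 1 - (10 + t)/50 = 78.0% (t = 1), 74.0% (t = 3).
- Censored: 80.0%.
- For secondary patency, assuming 10 abandonments before day 200 and t = 3: censored gives 80.0%; dropped gives 1 - 10/47 = 78.7%.

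**Against sampling error.** At 80% and N = 50 the 95% half-width is 1.96 × √(0.80 × 0.20/50) = 11.1 points. One to three such subjects (2 to 6 points) stay inside it.

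**Visit window.** Taking 3 months as day 91, the window runs from day 84 to day 105, centred on day 94.5. Trials of 50 were simulated assuming visits uniform over that window, 30%-50% of losses found only at visits, and half the subjects with no later visit. Reading the curve at day 91 by detection date was about 1.3 to 2.9 points high. Assigning 3-month visit outcomes to month 3 was 0.4 to 0.6 points low.

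**Optional follow-up.** Assume 88% patency at 3 months and 60% at 12 months, N = 50. If all are followed, the 12-month half-width is 1.96 × √(0.60 × 0.40/50) = 13.6 points. If half of the 44 still at risk continue (22), Greenwood's formula gives 1.96 × 0.60 × √(0.12/(0.88 × 50) + 0.318/(0.682 × 22)) = 18.2 points, with about 15 at risk.

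**The case against.** The strongest reply is that few analysts would carry a clotted access as patent. The curve is labelled patency, the same section judges patency by examination, and section 2.2 lists "Thrombosis (AVF completely clotted and cannot be used)", so such an access could be treated as abandoned. That reading is available, but it leaves the date open: occlusion, detection, decision or exit. It also asks the analyst to override a listed set of events that omits occlusion. The objection makes the worst case less likely; it does not make the rule clear.

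On transplant, exclusion criterion 11 (section 3.5.2) bars planned major surgery within 6 months of enrolment, which plausibly covers scheduled transplants. This stands: early transplant-related loss is probably uncommon, though unscheduled and later transplants remain possible.

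It is also fair that this is a descriptive pilot, that patency is two of eight listed endpoints, and that the case report forms are not in the documents and may record a date and reason for abandonment. These points limit the consequence. They do not supply the missing rules.

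A reader might infer that the plan will overstate patency, or might build a net bias range from assumed occlusion and transplant rates. The documents support neither: they give no such rates, and the two faults pull in opposite directions.

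**Conclusion.** The point holds as a defect in the stated rules. Followed literally, section 3.3 keeps a documented but untreated and undeclared occlusion in the patent group, dates a late-treated one late, and counts transplant-related loss of a patent access as a primary failure. Abandonment, the only secondary event, has no definition or date.

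The only size that rests on the documents is 2 points per affected subject, if 50 are enrolled and none is censored earlier; it is larger with fewer subjects. The number affected is not given and the net direction is unknown. The percentages in the illustrations depend on assumed event counts, visit patterns and patency rates.

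A reader might also infer that the 6- and 12-month estimates are biased because those visits are discretionary. The documents establish only a loss of precision; bias would follow if the discretion tracks fistula status, which they do not say. The wording should be changed, but no test or decision rule depends on it.

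**What to change.** Amend the two patency definitions in section 3.3:

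1. **Primary patency.** The event is the earliest of documented thrombosis or occlusion on examination, a patency intervention, or abandonment. Date an occlusion at its first documentation. Occlusion means no flow on duplex or angiogram; an absent bruit or thrill counts only if imaging does not contradict it. This is needed because the technical-success tests are alternatives that show patency and do not say what counts as its loss.
2. **Secondary patency.** Keep abandonment as the event, dated at the documented decision to stop using the access or not to restore it. If no decision is recorded and the access is never restored, date it at the first examination documenting the occlusion. Dating it at the last assessment would make the failure date depend on optional visits.
3. **Censoring, both curves.** A subject whose patent access is abandoned because of transplant is censored at transplant, not dropped. Otherwise, including death and loss to follow-up, censor at the last date patency was assessed.
4. **Reporting.** Report 3-month patency with the outcomes of the 3-month visit, events and censoring alike, assigned to month 3. Give any 6- or 12-month estimate with numbers at risk and a 95% confidence interval, labelled as based on optional follow-up.

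The cost is endpoint wording and possibly two case report form items (date of occlusion, reason for abandonment). No new tests are needed, since ultrasound up to 3 months is already required. The downside is that primary patency may read a few points lower.
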